5.5.11. Quality-of-Life (QoL) Analyses

For QoL summary, the analysis arm and methods are the same as the one used in the efficacy analysis.

For both EM and CM patients, descriptive summary based on 6 arms (LY120/LY120, LY240/LY240, PLA/LY120, PLA/LY240, CM120, CM240) will be shown.

In addition, for CM patients, the statistical models such as MMRM, GLIMMIX, and logistic regression will be used for some analysis with the treatment arm (CM120, CM240).

The analysis method and periods are specified in [Table CGAP. 5.5](#). MMRM, GLIMMIX, and logistic regression models are specified in [Section 5.5.1.1](#) and [Section 5.5.10](#).

5.5.11.1. MSQ

The mean change from baseline to each post-baseline visit for Study Period III for MSQ total score and domain (overall Month 1-12) will be analyzed by the MMRM model. The descriptive summary will be created (SP III/IV).

MSQ Role Function-Restrictive domain responders in SP III (month 12) will be analyzed by logistic regression. The descriptive summary will be created (SP III) (month 12).

Descriptive Summary of MSQ individual score (Q1 to Q14) will be created.

5.5.11.2. MIDAS

For SP III, the mean change from baseline to each post-baseline visit (month 3, 6, 9, 12) and overall will be analyzed by the MMRM model. (response variables are total score, each item 1, 2, 3, 4, 5, A, and B). The descriptive summary will be created (SP III/IV).

MIDAS responders ($\geq 50\%$ improvement in MIDAS total score) at each evaluated month, and overall) in SP III will be analyzed using GLIMMIX. Here overall is taken from the main effect of the model. The descriptive summary will be created (SP III).

5.5.11.3. HCRU

For HCRU, descriptive summary of Question 1-3 will be created. Analysis period is SP I/II/III/IV combined. It includes baseline (EM: CGAP Visit 3 data. CM: over the last 6 months period from Visit 3 data), SP III (12 months period), and SP IV (4 months period) with ITT population. In particular, for each period, the summary of following will be created:

- number of emergency room visits (Q1)
- number of emergency room visits related to migraine (Q1)
- number of overnight hospitalization (unit=incidence) (Q2)
- number of overnight hospitalization related to migraine (unit=incidence) (Q2)
- number of overnight hospitalization (unit=day) (Q2)
- number of overnight hospitalization related to migraine(unit=day) (Q2)
- number of healthcare professional visits (Q3)
- number of healthcare professional visits related to migraine (Q3)

Summary of HCRU related to migraine will be created (SP III/IV). The unit is per 100 patient years. 100 patient year is defined as

$$100 * (\text{sum of all events}) / (\text{number of total months with patient data} / 12).$$

Descriptive summary of working status (Question 4) will be created for each month: Analysis period is SP III/IV combined. It includes month 0 to month 12, month 14, and month 16 with ITT population.

5.5.11.4. PSMQ-M

Summary of each item, as well as positive response defined in Section 5.4.3.4 will be created using descriptive statistics for each month (month 1, 6, 12, 16) in SP III/IV.

5.5.12. Safety Analyses

The safety analyses will be conducted for Study Period III, Study Period IV, as well as Study Periods III and IV combined. Treatment group is based on 4 arms (EM120, EM240, CM120, CM240), unless otherwise specified. AE related tables will be sorted by LY_ALL. In such cases, LY_ALL will be displayed in the table.

The safety and tolerability of treatment will be assessed by the followings:

- Adverse events
 - hypersensitivity events
 - injection sites
 - upper respiratory tract infections
- Suicide-related thoughts and behaviors
- Vital signs and weight
- Laboratory measurements
- ECGs
- Antibodies (ADA and NAb)

The baseline and post-baseline for safety measures are described in [Table CGAP. 5.4](#), unless otherwise specified.

For laboratory, vital, weight, ECG and ADA, categorical and/or continuous analysis will be conducted. Detail analysis are specified in the following sections.

5.5.12.1. Categorical Safety Variables

Unless specified otherwise, the categorical safety analyses will include both scheduled and unscheduled visits. Unless otherwise specified, categorical safety analyses will only be conducted for Study Period III and Study Period IV separately.

Comparisons between treatment groups for all categorical safety measures will be made using the Fisher's exact test for Study Period III with the safety population, unless otherwise specified.

Descriptive statistics only will be presented for the treatment groups in Study Period IV with the post-treatment population.

5.5.12.1.1. Adverse Events

Treatment-emergent adverse events are defined as the reported AEs that first occurred or worsened during the post-baseline phase compared with the baseline phase. Pre-existing condition that is still ongoing at Visit 1 for CM patients should be evaluated as baseline values. For each TEAE, the severity level of the event (mild, moderate, or severe) will be determined by patient or physician opinion. The MedDRA Lowest Level Term (LLT) will be used in the treatment emergent computation. For each LLT, the maximum severity at baseline will be used as the baseline severity. If the maximum severity during post-baseline is greater than the maximum baseline severity, the event is considered to be treatment-emergent for the specific post-baseline period. For each patient and TEAE, the maximum severity for the MedDRA level being displayed (PT, High Level Term, or SOC) is the maximum post-baseline severity observed from all associated LLTs mapping to that MedDRA level.

Follow-up emergent adverse events (post-treatment emergent adverse events) are defined similarly. They are events that first occurred or worsened during the follow-up period (Study Period IV) when compared to the baseline (SP I, SP II, and SP III). Pre-existing condition that is still ongoing at Visit 1 for CM patients should be evaluated as baseline values. (See detail definitions in [Table CGAP. 5.4](#))

For events that are gender-specific, the denominator and computation of the percentage will include only patients from the specific gender.

Following summary will be created:

- Overview of AE (SP III)
- TEAEs (SP III)
 - By PT by decreasing frequency
 - By SOC/PT
 - By maximum severity/PT
- FEAEs (SP IV)
 - By PT by decreasing frequency
 - By SOC/PT
 - By maximum severity/PT
- TEAEs by considered to be related to investigational product by investigator (SP III)
- Treatment Emergent Adverse Events that started on Treatment phase and Continuing in Post-Treatment Phase (SP III, SP IV combined)
- SAEs (SP III, SP IV separately)
- AEs leading to discontinuation (SP III, SP IV separately)

Following tables are created by 6 arms (with LY_ALL) without statistical tests:

- TEAEs (SP III) by SOC/PT
- TEAE by considered to be related to investigational product by investigator (SP III)

Listing of Subjects with TEAE or FEAE (SP III, SP IV combined) will be created.

Listing of Adverse Events Leading to Discontinuation and Serious Adverse Events (SP I, SP II, SP III, SP IV combined) will be created.

5.5.12.1.1.1. Potential Hypersensitivity events

Potential hypersensitivity events (immediate and no immediate) will be identified from a review of preferred terms generated from the following queries:

- Broad and narrow terms in the Anaphylactic reaction SMQ (20000021)
- Broad and narrow terms in the Angioedema SMQ (20000024)
- Broad and narrow terms in the Hypersensitivity SMQ(20000214)

Summary for the potential hypersensitivity events (SP III) will be created. These analyses will be medically reviewed to determine if the terms identified represent actual hypersensitivity events before DBL. Only those that are judged medically to be hypersensitivity events will be included in the tables of “hypersensitivity events”.

The number and percentage of patients with TEAEs (SP III) and AEs resulting in study drug discontinuation (SP III) will be summarized by treatment groups using MedDRA PT nested within the SMQ. Events will be ordered by decreasing frequency within the SMQ.

The number and percentage of patients with treatment-emergent hypersensitivity events by maximum severity (SP III) will be summarized by treatment groups using MedDRA PT.

The number and percentage of patients with TEAEs hypersensitivity events by timing (SP III) will be summarized using MedDRA PT nested within the SMQ. Events will be ordered by decreasing frequency. Note the timing of the hypersensitivity events is collected through eCRF and categorized into the following categories:

- During drug administration

- Within 30 minutes of end of study drug administration
- 30 minutes and up to 6 hours from end of study drug administration
- 6 hours and up to 24 hours from end of study drug administration
- 24 hours and up to 14 days from end of study drug administration
- Greater than 14 days from end of study drug administration

If these information was not collected, then such data will be excluded from the timing analysis.

The relationship between the development of treatment-emergent hypersensitivity events and TEAEs related to injection sites (SP III) will be summarized.

A listing of Subjects with Treatment-Emergent or Post-Treatment Emergent Potential Hypersensitivity Events will be created.

Figure of duration of Potential Hypersensitivity Events for each PT (SP III/IV) will be created.

5.5.12.1.1.2. Adverse Events Related to Injection Site

Adverse events related to injection sites will be defined using terms from the MedDRA High Level Term “Injection Site Reactions”.

The number and percentage of patients with TEAEs related to injection sites (SP III) and AEs related to injection sites resulting in study drug discontinuation (SP III) will be summarized using MedDRA PT. Events will be ordered by decreasing frequency within High Level Term.

The number and percentage of patients with TEAEs related to injection sites by maximum severity (SP III) will be summarized by treatment groups using MedDRA PT. For each patient and AEs related to injection sites, the maximum severity for the MedDRA level being displayed (PT) is the maximum post-baseline severity observed from all associated LLTs mapping to that MedDRA level.

The number and percentage of patients with TEAEs of injection sites by timing (SP III) will be summarized using MedDRA preferred terms ordered by decreasing frequency. Note the timing of injection site reactions is collected through eCRF and categorized as follows:

- Occurs during study drug administration
- Occurs within minutes (<60 minutes) of study drug administration
- Occurs from 1 up to 6 hours of study drug administration
- Occurs from >6 hours through 14 days from study drug administration, which will be split into two categories: on the same day of injection and after the day of injection
- Occurs >14 days of study drug administration

If these information was not collected, then such data will be excluded from the timing analysis.

Listing of Subjects with Treatment-Emergent Adverse Events Related to Injection Sites will be created.

Summary of Injection Site Reaction by Max Severity, by Anatomical Location (Abdomen, Arm, Buttock, and Thigh) will be created.

Figure of duration of Injection Site related Adverse Events for each PT (SP III/IV) will be created.

5.5.12.1.1.3. Upper Respiratory Tract Infections

Upper respiratory tract infections will be defined using all the PTs from the 2 high level terms of “upper respiratory tract infections” and “upper respiratory tract infections NEC” as defined in MedDRA.

The number and percentage of patients with TEAEs of Upper respiratory tract infections (SP III and SP IV separately) and resulting in study drug discontinuation (SP III) will be summarized by treatment group using MedDRA PTs. Events will be ordered by decreasing frequency.

The number and percentage of patients with TEAEs of upper respiratory tract infections by maximum severity (SP III) will be summarized by treatment groups using MedDRA PT. For each patient and upper respiratory tract infection event, the maximum severity for the MedDRA level being displayed (PT) is the maximum post-baseline severity observed from all associated LLTs mapping to that MedDRA level.

Listing of Subjects with Treatment-Emergent or Post-Treatment Emergent Upper Respiratory tract infection (SP III, SP IV combined) will be created.

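### As worded, the displayed severity of a treatment-emergent event is the maximum over all LLTs under the term, so a non-emergent LLT can raise the grade of a new, milder event.

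*SAP*

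**What the plan says.** SAP section 5.5.12.1.1 works at two levels. Emergence is decided at the lower one: "The MedDRA Lowest Level Term (LLT) will be used in the treatment emergent computation". The reference is also set there: "For each LLT, the maximum severity at baseline will be used as the baseline severity". The test is a strict increase: "If the maximum severity during post-baseline is greater than the maximum baseline severity, the event is considered to be treatment-emergent".

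Severity for display is set at the higher level. The sentence begins "For each patient and TEAE, the maximum severity for the MedDRA level being displayed (PT, High Level Term, or SOC" and ends by saying that this severity "is the maximum post-baseline severity observed from all associated LLTs mapping to that MedDRA level". Follow-up emergent events (FEAEs) are defined in the same way, with SP I to SP III as baseline. For both TEAEs and FEAEs the section lists a summary "By maximum severity/PT".

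The display rule is repeated in 5.5.12.1.1.2 for injection-site events ("the maximum severity for the MedDRA level being displayed (PT) is the maximum post-baseline severity observed from all associated LLTs") and in 5.5.12.1.1.3 for upper respiratory infections ("For each patient and upper respiratory tract infection event, the maximum severity for the MedDRA level being displayed (PT"). In these two places the lead-in speaks of AEs and of an event, not of a TEAE. Section 5.5.12.1.1.1 plans a maximum-severity table for hypersensitivity events and states no derivation of its own.

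**The concern.** The same section defines a TEAE as something that is new or has worsened since baseline. A table of TEAEs by maximum severity should therefore show how severe the new or worsened event was. As worded, the grade may come from an LLT that neither appeared nor worsened after baseline. The table could then report a severe TEAE in a patient in whom nothing severe emerged.

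Safety and tolerability is the primary objective, and TEAEs are its first listed endpoint (SAP Table CGAP.4.1). With about 30 patients per CM arm and 120 per EM arm, one or two re-graded patients can change a row for severe events. Two programmers could also produce different tables from this text.

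**Working it through.** **1. Worked case.** Two LLTs map to one PT.

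| | Baseline | Post-baseline | Emergent? |
|---|---|---|---|
| LLT-1 | severe | severe | no (not greater) |
| LLT-2 | none | mild | yes |

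The maximum over all LLTs is severe. The maximum over emergent LLTs is mild.

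**2. All possible patterns.** Score severity 0 to 3 (none, mild, moderate, severe) for each LLT at baseline and post-baseline. An LLT is emergent if post > baseline. Compare max(post) over all LLTs with max(post) over emergent LLTs.

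| LLTs under the PT | Patterns with an emergent LLT | Displayed grade too high | Displayed grade too low | Worst emergent LLT mild, shown higher |
|---|---|---|---|---|
| 1 | 6 | 0 | 0 | 0 of 1 |
| 2 | 156 | 10 | 0 | 6 of 21 |
| 3 | 3096 | 300 | 0 | 162 of 331 |

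So the error needs at least two LLTs and only runs upward. These are counts of possible patterns, not expected frequencies.

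**3. Possible size.** The documents give no event rates, so this is a simulation on assumptions: two LLTs per PT (split 70/30 or 85/15), severity 75/20/5% mild/moderate/severe, independent reactions, 6 injection visits in the baseline window, 12 in SP III, 200,000 patients per scenario.

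| Reaction probability per visit | Patients reacting in SP III, 1 − (1 − p)^12 | TEAE patients shown too high |
|---|---|---|
| 0.02 | 22% | about 0.01% to 0.02% |
| 0.05 | 46% | about 0.1% to 0.2% |
| 0.1 | 72% | 0.5% to 0.6% |
| 0.2 | 93% | 2.3% to 2.4% |
| 0.3 | 99% | 4.5% to 5.1% |
| 0.5 | nearly 100% | 7% to 11% |

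With no injections in the baseline window the result is 0% throughout. For p from 0.1 to 0.5, the share shown as moderate or severe rises by 0.5 to 10 percentage points.

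In patients per EM arm of 120, with the simulated share having a TEAE:
- all patients at p = 0.1: 120 × 0.59 × 0.0063 ≈ 0.4;
- all patients at p = 0.05: 120 × 0.41 × 0.0014 ≈ 0.07;
- an assumed reaction-prone 10% (12 patients) at p = 0.3 to 0.5: from 12 × 0.73 × 0.046 ≈ 0.4 to 12 × 0.72 × 0.109 ≈ 0.9.

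**4. Who is exposed.** For SP III TEAEs, SAP Table CGAP.5.4 sets the EM baseline from CGAN Visit 1 to CGAP Visit 3. That window contains the parent study's treatment phase (section 5.5.4 refers to CGAN Month 6). CM patients have Visits 1 to 3 only and receive their first study injection at Visit 3. Injection-site over-grading in SP III can therefore arise in EM patients but not in CM patients. For SP IV the baseline includes all of SP III in both populations, so FEAE severity is exposed in every arm.

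**The case against.** The best reply is that the SAP already means emergent LLTs only. The sentence in 5.5.12.1.1 is introduced by patient and TEAE, the LLT has just been fixed as the unit of emergence, and the tables are titled as TEAE tables. The associated LLTs could then be those that make up the TEAE. This may well be the intent, so a reader should not infer that the sponsor set out to mix in non-emergent terms. But the restriction is not written, and the injection-site and upper respiratory sections lack even that lead-in.

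The second reply is that the effect is small and conservative: it shows a grade the patient did have under that PT after baseline, and the planned listings allow a check. That stands as a limit on importance. It does not make the table match its title.

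The third is that restricting the maximum makes the PT grade depend on which near-synonymous LLT was coded. True, but the SAP's emergence rule already has that dependence.

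Two stronger readings are tempting, and the documents do not support either.
- **That the treatment comparisons are biased.** Section 5.5.12 sets safety tables at four arms, and section 5.5.1 compares only EM120 with EM240 and CM120 with CM240. Each pair shares one baseline window, and each EM arm pools LY/LY with PLA/LY patients. The two six-arm AE tables are not severity tables.
- **That only LY/LY patients are exposed.** PLA/LY patients come from the placebo arm of a double-blind study and presumably also had injections, and possibly reactions, in the baseline window.

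**Conclusion.** The concern holds as a defect of wording that should be corrected. Followed literally, a non-emergent LLT can raise the displayed severity of a new, milder TEAE or FEAE. The error is upward only, needs two or more LLTs under one PT, and is confined to the maximum-severity tables.

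Its size is probably small, but the documents cannot settle it. The 0.5% to 11% range applies to assumed reaction-prone patients, whose share is unknown, and must not be read as a trial-level rate. At per-visit probabilities of 0.05 and below the figure is about 0.2% or less.

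No known direction of bias follows for EM120 vs EM240 or CM120 vs CM240. What remains is the side-by-side display in SP III, where EM severity can look higher than CM severity because the EM baseline covers the parent study's injection period. That applies to all EM patients injected there.

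**What to change.** In SAP 5.5.12.1.1, 5.5.12.1.1.2 and 5.5.12.1.1.3, state that the maximum is taken only over LLTs that are treatment-emergent (for SP IV, follow-up emergent) in the period and that map to the displayed level. State the same rule for the hypersensitivity maximum-severity table in 5.5.12.1.1.1. If the narrower reading was always intended, this only records it. If the sponsor does want all post-baseline LLTs, a footnote to each table should say that the grade may come from a non-emergent term.

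The cost is one phrase in three sections, one sentence in the fourth, and one filter in the program. No new data are needed, and no incidence table changes.

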5.5.9. Concomitant Therapy, Migraine Prevention Therapy, and Migraine Acute Treatment

For concomitant therapy summary, treatment group is based on (EM120, EM240, CM120, CM240)

The proportion of patients who received concomitant medication will be summarized for ITT patients for Study Period III and for the post-treatment population for Study Period IV separately. The concomitant therapy does not include migraine acute (abortive) treatments or migraine prevention therapy.

Concomitant therapies for study period III are those which started, stopped or continued in study period III. If medication started and stopped on the same day of injection, it will still be considered as concomitant medication for SP III. If medication started before the first day of injection but stopped on the same day of injection, then it will not be counted as concomitant medication for SP III.

Concomitant therapies for study period IV are those which either started, stopped or continued in Study Period IV. If medication started and stopped on the first day of SP IV, it will still be considered as concomitant medication for SP IV.

Treatment group comparisons will be done using the Fisher's exact test for Study Period III with ITT population. Descriptive statistics only will be presented for the treatment groups in Study Period IV with the post-treatment population.

Similar outputs for migraine prevention therapy will be created for SP III and SP IV. As mentioned in the previous section, the definition of the prevention therapy will be reviewed by medical before unblinding

Similar outputs for migraine acute treatment will be created for SP III and SP IV separately. The categorization is based on Section 5.5.8.

As mentioned in the previous section, the definition/categorization of the migraine prevention therapy and migraine acute treatments will be reviewed by medical before unblinding.

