5.6. Interim Analyses

At least 1 interim analysis is planned after the database lock for Study CGAN. The interim analysis will be conducted to support regulatory submission prior to all patients completing the CGAP study.

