5.7. Unblinding Plan

CGAP is an open label study. However EM patients' injection at CGAP Visit 3 will be kept blind until the earliest timing of an interim CGAN database lock (DBL) (if it takes place), the final CGAN DBL, or the interim CGAP DBL (if it takes place).

The earliest timing of the interim CGAP DBL (if it takes place) or the final CGAP DBL will be equal to or later than the earliest timing of the interim CGAN DBL (if it takes place) or the final CGAN DBL. This guarantees that all CGAN patients finish the CGAN double blind treatment period (Study Period III) and the data in CGAN Study Period III is locked.

When the interim CGAN DBL, the final CGAN DBL, or the interim CGAP DBL takes place, then an unblinding occurs. The unblinding will reveal the CGAP Visit 3 injection, as well as CGAN treatment arms for EM patients.

During the CGAP study, some members are unblinded ([Table CGAP. 5.8](#)). They do not have direct interaction with sites. They will not be allowed to join meetings which may affect the

other members' blind condition, such as trail level safety review (TLSR) and data review meetings.

Table CGAP. 5.8 Unblinded Members through CGAP Study

Role	Reason	Data source for unblinding
Product Delivery personnel	To provide and manage Clinical trial materials	e-CTS
Clinical Laboratory Operations	To manage and track sample shipping	CLRM
Unblind Case Manager	To report SAE with unblinded information to EU authority	e-CTS
Data Movement	To transfer unblinded data at the timing of the interim CGAN DBL, the final CGAN DBL, or the CGAP interim DBL	source data of CLUWE

Abbreviations: CLRM = Clinical Laboratory Results Modernization; DBL = database lock; e-CTS = Enhanced Clinical Trials System; EU = European Union; GPS = Global Patient Safety; IWRS = interactive web-response system; PK/PD = pharmacokinetics/ pharmacodynamics; SAE = Serious Adverse Event.

The CGAP interim analysis will be conducted by the CGAP unblinded study members. They do not have direct interaction with sites ([Table CGAP. 5.9](#)) after the unblinding. These members will become unblinded after the earliest timing of the interim CGAN DBL, the final CGAN DBL, or the CGAP interim DBL. All study personnel with direct interaction with sites after the unblinding are kept blinded to the interim analysis results.

Table CGAP. 5.9 Unblinded Members Unblinded after the Earliest Timing of the Interim CGAN DBL, the Final CGAN DBL, or the CGAP Interim DBL

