Role	Reason	Data source for unblinding
Project Statistician	CSR/PMDA consultation preparation	CLUWE/TFL
Statistical Analyst	CSR/PMDA consultation preparation	CLUWE/TFL
Statistical Analysis programmers	CSR/PMDA consultation preparation	CLUWE/TFL
Medicals (Clinical Research Scientist, Clinical Research Physician)	CSR/PMDA consultation preparation	TFL
PK/PD	CSR/PMDA consultation preparation	CLUWE/TFL
Medical Writer	CSR/PMDA consultation preparation	TFL
CPM	CSR/PMDA consultation	TFL

	preparation	
CTPM	CSR/PMDA consultation preparation	TFL
PPM	CSR/PMDA consultation preparation	TFL
Regulatory	CSR/PMDA consultation preparation	TFL
Data Management	CSR/PMDA consultation preparation	CLUWE/TFL

Abbreviations: CPM = Clinical Project Manager; CTPM = Clinical Trial Project Manager; CSR = Clinical Study Report; TFL = tables, figures, listings; PK/PD = pharmacokinetics/pharmacodynamics; PPM = Product Project Manager; CLUWE = Clinical Users Working Environment;

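### Medical reviews that settle which hypersensitivity events and migraine therapies are tabulated are not masked to arm, and the SAP's condition that the therapy review precede unblinding cannot be met for the final lock

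*SAP*

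**What the plan says.** Two separate medical reviews are involved.

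**Hypersensitivity (SAP 5.5.12.1.1.1).** Candidate events come from three standardised MedDRA queries. Then: "Summary for the potential hypersensitivity events (SP III) will be created". Next: "These analyses will be medically reviewed to determine if the terms identified represent actual hypersensitivity events before DBL". The outcome decides what is tabulated: "Only those that are judged medically to be hypersensitivity events will be included in the tables of" hypersensitivity events. SAP 5.5.12 sets the layout of safety summaries: "Treatment group is based on 4 arms (EM120, EM240, CM120, CM240), unless otherwise specified". The hypersensitivity section makes no exception for the summary that is reviewed.

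**Migraine therapies (SAP 5.5.8 and 5.5.9).** Section 5.5.9 says that "the definition/categorization of the migraine prevention therapy and migraine acute treatments will be reviewed by medical before unblinding". Section 5.5.8 describes the same review and places it before database lock.

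**Who is unblinded, and when (SAP 5.6 and 5.7).** Table CGAP. 5.9 lists "Medicals (Clinical Research Scientist, Clinical Research Physician") with the tables, figures and listings as their data source. On timing: "These members will become unblinded after the earliest timing of the interim CGAN DBL, the final CGAN DBL, or the CGAP interim DBL". Section 5.6 adds: "At least 1 interim analysis is planned after the database lock for Study CGAN".

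**The concern.** Whether an event picked up by a broad query is a true hypersensitivity event is a matter of judgement. So, to a lesser degree, is whether a drug was taken for prevention or as acute treatment. Such judgements are safest when the person making them cannot see the arm. The SAP does not arrange this for hypersensitivity, and for therapies it sets a timing that its own unblinding plan rules out.

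At stake is how freely the reviewed hypersensitivity tables can be trusted. Hypersensitivity is one of the adverse-event topics listed in SAP 5.5.12. Under SAP 5.5.12.1, categorical safety measures in Study Period III are compared between groups by Fisher's exact test, at two-sided 0.05 with no multiplicity adjustment (5.5.1). A term that is concentrated in one dose group could be kept or dropped by someone who can see that concentration.

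**Working it through.** No stated figure is in dispute. The check is one of sequence, followed by an illustration of sensitivity.

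**Step 1: order of events.**
1. The first CGAP lock is no earlier than the first CGAN lock (SAP 5.7).
2. The medical role is unblinded after the earliest of the interim CGAN, final CGAN and interim CGAP locks (5.7, Table CGAP. 5.9).
3. The CGAP interim tables cover all Study Period III safety data to date, including treatment-emergent events by preferred term (5.8.1).
4. SAP Version 3 was written after preliminary results from the interim lock had been reviewed (5.5).
5. The final lock follows.

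Any review done between steps 4 and 5 therefore comes after step 2. For data that accrued after the first lock, a review by these staff before unblinding is impossible. Even for the CGAP interim lock, they may already have been unblinded by an earlier CGAN lock. Dose is in any case open from Visit 5 (SAP 5.1.1 and 5.1.2).

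**Step 2: the two timing statements for therapies.** Section 5.5.8 requires the review before database lock, which can still be met at the final lock. Section 5.5.9 requires it before unblinding, which cannot. The two sections describe one review and need one rule.

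**Step 3: what the hypersensitivity reviewer sees.** The material is the potential-event summary. Under the 5.5.12 default it has four arms. The only stated constraint is that review precedes a database lock, and which lock is not said. Nothing prevents the arm split from being in view.

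**Step 4: sensitivity of the Fisher comparison.** Planned arm sizes are 120 and 120 for EM (SAP 5.2.1) and 30 and 30 for CM (5.2.2). The event counts are assumptions; the documents give none. Two-sided Fisher's exact test on the table [a, n−a; b, n−b]:

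| n per arm | Counts | p | After reclassification | p |
|---|---|---|---|---|
| 120 | 10 vs 2 | 0.034 | 9 vs 2 | 0.059 |
| 120 | 10 vs 2 | 0.034 | 8 vs 2 | 0.102 |
| 120 | 6 vs 0 | 0.029 | 5 vs 0 | 0.060 |
| 30 | 6 vs 0 | 0.024 | 5 vs 0 | 0.052 |
| 120 | 12 vs 2 | 0.011 | 10 vs 2 | 0.034 |
| 120 | 8 vs 4 | 0.375 | 7 vs 4 | 0.539 |

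The first four rows were chosen at the 0.05 boundary, and there one or two patients change the side of the line. In the last two rows they do not.

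**The case against.** Much can fairly be said for the plan.

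- **No broken promise on hypersensitivity.** That section commits only to review before lock. It does not claim blinding and names no reviewer. This stands. The defect is that masking and reviewer are unspecified. A reader might infer from Table CGAP. 5.9 that the unblinded medical staff do the review. That is the natural reading, but the SAP does not say it.
- **The judgement is about terms.** A term kept or dropped is kept or dropped in all arms, so single patients cannot be picked out of one arm. This limits the bias. It does not remove it, since a term's arm split can be visible when the decision is made, and the sentence on which events qualify can also be read event by event.
- **Not a primary-objective item.** A reader might infer that hypersensitivity is named in the primary objective. Table CGAP. 4.1 does not name it; it appears only as an adverse-event topic in 5.5.12.
- **No interim hypersensitivity table.** A reader might infer that reviewers have already seen hypersensitivity results by arm. The list in 5.8.1 has no such table, only treatment-emergent events by preferred term.
- **Exclusions can be traced.** A potential-event summary, a listing and a duration figure are already planned. This stands, but the SAP does not ask for the potential-event summary to be reported beside the reviewed table.
- **Therapy classes leave little discretion.** Acute treatments fall into drug classes, and medication-day endpoints come from diary counts (5.4.1). No effect on an efficacy endpoint is shown.
- **Open label, two active doses.** True, and no decision rule rests on these p-values. Yet the SAP itself keeps an unblinding plan and ties one review to it.

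**Conclusion.** The point holds as a cheap improvement. Two findings are firm. First, 5.5.9 conflicts with 5.5.8, and given 5.7 and Table CGAP. 5.9 its timing cannot be met by the listed medical staff for data reviewed for the final lock. Second, 5.5.12.1.1.1 lets a medical judgement determine the hypersensitivity tables without naming a reviewer or withholding arm.

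That the reviewed summaries are by arm rests on the 5.5.12 default. That the reviewers are the Table CGAP. 5.9 medical staff rests on natural reading.

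The size of any bias is unknown. The p-values show only that a count near 0.05 is fragile. They do not support a claim that reclassification would decide the result, and the documents give no sign that any event has been misclassified.

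**What to change.** In SAP 5.5.8, 5.5.9 and 5.5.12.1.1.1, replace the reference to reviewing the analyses, and the condition about unblinding, with one rule:

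- Review is made on listings of terms, events and medications that omit arm, cohort, dose and number of injections.
- Decisions are dated and fixed before any by-arm hypersensitivity or therapy table of that lock is run.
- The lock meant, interim or final, is stated, and so is the role that does the review.
- Any decisions already made at the interim are carried forward unchanged.
- The potential-event summary already planned is reported by arm beside the reviewed hypersensitivity table.

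The cost is SAP wording and unlabelled listings, with no extra staff. The drawback is that masking is only partial, because the medical staff may have seen the interim tables of events by preferred term. The side-by-side display helps there, since it shows the reader what the review removed.
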